### **9.3.4 Pharmacokinetic Analyses**

Analyses will be carried out on the PK analysis population. PK parameters will be estimated using a population PK model and presented by listings and descriptive summary statistics (mean, standard deviation, coefficient of variation, median, minimum, and maximum).

The plasma concentration of basmisanil and its major metabolite M1 will be determined. PK parameters for basmisanil are  $AUC_{\text{tau,ss}}$ ,  $C_{\text{max,ss}}$ ,  $C_{\text{trough,ss}}$ ,  $CL/F$ , and  $Vd/F$  will be estimated by using population PK analysis. Plasma concentration ratio of M1 to basmisanil at trough will be determined as well as other PK parameters as appropriate.

Estimates for these parameters will be tabulated and summarized.

The population PK analysis analyses will be presented separately from the main CSR.

### **9.3.5 Pharmacodynamic Analyses**

The main PD endpoint is the change in the characteristic Dup15q EEG phenotype, acutely and at steady state.

Results for change in EEG beta-band power from baseline will be presented in summary tables, graphs, and listings.

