Clinically, basmisanil decreases  $\text{GABA}_\text{A}$   $\alpha 5\text{R}$  function in the brain, as indexed by the decreases in EEG beta-band power (see the [Basmisanil Investigator's Brochure](#)). This provides PD evidence that basmisanil can directly target  $\text{GABA}_\text{A}$ -related pathomechanisms in Dup15q syndrome, namely excessive  $\text{GABA}_\text{A}$   $\alpha 5\text{R}$  activity. This study will use EEG beta-band power as a marker of excess  $\text{GABA}_\text{A}$ R function in Dup15q syndrome (see Section 2.2.3). In particular, this study will test for treatment-related quantitative EEG (qEEG) normalizations to increase the confidence that the selected dose of basmisanil affects the  $\text{GABA}_\text{A}$ R-related pathophysiology. In case of lack of effects of basmisanil treatment on the Dup15q EEG phenotype at an early interim analysis, which would point to lack of beneficial effects on the GABA-related pathophysiology, the study would be stopped to ensure that participants are not treated unnecessarily (see the interim analyses in Section 4.1.2.2).

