**Table 5 Objectives and Endpoints for Part 1 (cont.)**

Objectives	Endpoints
Secondary (cont.)	
Safety (cont.)	

 
To evaluate the tolerability and safety of 52 weeks of treatment with basmisanil
 
	
 
Abnormal changes in EEG recordings compared to baseline with a focus on treatment-emergent epileptiform abnormalities
 
Systolic and diastolic blood pressure and heart rate measurements
 
Suicidality as assessed through questions from selected items adapted from the C-CASA in participants aged 6 years and above
 
Height, weight, head circumference
 
Tanner staging over time (in participants aged 9 years and above)
 

PK	

 
To characterize the PK of basmisanil and its metabolite M1 [REDACTED]
 
To evaluate potential relationships between selected covariates and exposure to basmisanil
 
	
 
Plasma concentration of basmisanil and its major metabolite M1 at specified timepoints.
 
PK parameters for basmisanil: <math>AUC_{\text{tau,ss}}</math>, <math>C_{\text{max,ss}}</math>, <math>C_{\text{trough,ss}}</math>, <math>CL/F</math>, <math>Vd/F</math>
 
Plasma concentration ratio of M1 to basmisanil at trough
 
PK parameters for M1: <math>C_{\text{max,ss}}</math>, <math>C_{\text{trough,ss}}</math>
 
Other PK parameters as appropriate
 

PD	

 
To evaluate the effects of basmisanil treatment on the characteristic Dup15q EEG phenotype acutely and at steady state
 
	
 
qEEG beta-band power
 

$AUC_{\text{tau,ss}}$  = area under the concentration–time curve during one dosing interval at steady state;  
 C-CASA = Columbia Classification Algorithm for Suicide;  $CL/F$  = apparent clearance;  $C_{\text{max,ss}}$  = maximum concentration at steady state;  $C_{\text{trough,ss}}$  = trough plasma concentration at steady state;  
 PD = pharmacodynamics; PK = pharmacokinetics; qEEG = quantitative EEG;  $Vd/F$  = apparent volume of distribution.

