#### **Interim analyses:**

In addition to the aforementioned reviews of PK and safety data, the IMC+SOC will also oversee up to two interim analyses:

- The **first interim analysis** occurs once approximately 24 participants (i.e., the participants of Stages 1 and 2), with a minimum of 9 participants aged 2 to 5 years, have completed 4 weeks of treatment. In addition to PK, safety, and tolerability data, the IMC+SOC will review the effect of basmisanil treatment on the Dup15q EEG phenotype (qEEG beta-band power).  
The IMC may recommend continuing the study unchanged, to adapt the dose, to decrease PK and/or safety assessments, or to stop the study in case of significant safety findings or in case of lack of effect of basmisanil treatment on the Dup15q EEG phenotype.
- A **second interim analysis** may occur as described in Section 9.5. Following review of the data, the IMC may recommend to continue the study unchanged or to terminate the study if benefit / risk considerations make a continuation unethical.

The study will continue to enroll participants during the conduct of both interim analyses. Details of interim analyses will be described in a technical document, which will be stored in the Sponsor's trial master file.

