###### Biomarker: Quantitative EEG

The background EEG in the awake state of individuals with Dup15q syndrome shows markedly abnormal (excess) beta-band power and is thought to index excess GABAA neurotransmission (Urraca et al 2013, Frohlich et al 2016, Frohlich et al 2019). This EEG abnormality will be quantified (qEEG) at several timepoints (qEEG blocks) to test for treatment-related changes (see Section 8.6.2).

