### **8.6.2 Effect of Basmisanil on the EEG (qEEG) Assessments**

EEG will be measured at clinic visits according to the SoA (see Section 1.3) using a clinical EEG system (10/20 montage comprising up to 32 electrodes plus auxiliary channels such as electrooculogram [EOG] or ECG).

Sections of the EEG data at pre-defined times (*qEEG blocks*, see [Table 2](#) and [Table 4](#) for Part 1 and Part 2, respectively) will be used for quantitative analyses. The impedance of electrodes will be checked before starting each block and participants will be instructed to remain as calm as possible and awake during the *qEEG block* with the goal to achieve good data quality for quantitative analysis. Recording good quality EEG data will be challenging but should be attempted. The EEGs will be used to evaluate the effect of basmisanol treatment on *EEG beta-band power*, acutely and at steady state, and to relate these signals to the *PK data*. In particular, the treatment-related change in the EEG beta-band power from Baseline to Day 2 and to Day 14 will be investigated (see Section 9.3.5).

For EEG to monitor safety see Section 8.2.9.

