### **9.3 STATISTICAL ANALYSES OF PART 1**

#### **9.3.1 Demographics and Baseline Characteristics**

Demographic and baseline characteristics will be summarized by treatment group using means, standard deviations, medians, and ranges for continuous variables and proportions for categorical variables, as appropriate. Analyses will be performed in all randomized participants and in the intent-to-treat (ITT), if different.

Baseline will be defined as the latest available value prior to the first dose of study treatment.

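### As visible, Section 9.3.5 only summarises change in qEEG beta-band power: add (or cross-refer to) a baseline-adjusted between-arm contrast and name the qEEG baseline recording

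*Combined protocol and SAP*

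**What the plan says.** Table 5 lists qEEG beta-band power under a secondary objective: "To evaluate the effects of basmisanil treatment on the characteristic Dup15q EEG phenotype acutely and at steady state". Two rationale sections promise a test. Section 2.3.2 says that "this study will test for treatment-related quantitative EEG (qEEG) normalizations", and Section 4.2.3.1 says the EEG abnormality "will be quantified (qEEG) at several timepoints (qEEG blocks) to test for treatment-related changes".

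Section 8.6.2 names the comparisons: the "treatment-related change in the EEG beta-band power from Baseline to Day 2 and to Day 14 will be investigated". It then sends the reader to Section 9.3.5. That section calls the change in the EEG phenotype the main PD endpoint, and its only statement on method is "Results for change in EEG beta-band power from baseline will be presented in summary tables, graphs, and listings".

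The general baseline rule is in Section 9.3.1: "Baseline will be defined as the latest available value prior to the first dose of study treatment".

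The result also feeds a decision. Under Section 4.1.2.2, at the first interim analysis (about 24 participants with 4 weeks of treatment), the monitoring committee may recommend stopping the study "in case of lack of effect of basmisanil treatment on the Dup15q EEG phenotype".

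**The concern.** A reader who follows the promise of a test from Sections 2.3.2, 4.2.3.1 and 8.6.2 to Section 9.3.5 finds no test and no estimate comparing the arms. Tables, graphs and listings of change from baseline do not commit the sponsor to a basmisanil-minus-placebo difference with a stated uncertainty. This endpoint is the study's evidence that the drug acts on the target pathophysiology, and it is reviewed when about 8 placebo participants are available. Raw change also carries the full noise of the baseline recording, which matters because Section 8.6.2 itself warns: "Recording good quality EEG data will be challenging but should be attempted".

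The baseline is also unclear. Section 8.6.2 speaks of change from Baseline, which in Table 1 is a visit between Day -7 and Day -1. Section 9.3.1 would instead select a Day 1 pre-dose block if one is scheduled. The two rules can yield different numbers for the same participant.

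**Working it through.** **1. The plan's own figures.** Section 9.1: 90 × (1 − 0.10) = 81 evaluable, which reproduces. At 2:1 this is 54 vs 27. The first interim at about 24 is 16 vs 8. The documents give no SD, effect size or power for qEEG, so the figures below are in SD units. The correlation rho between recordings and equal variances are assumptions.

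**2. Raw change against adjustment for one baseline.**

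- Per-participant variance of raw change: 2(1 − rho).
- Residual variance after adjusting for one baseline: 1 − rho².
- Finite-sample factor for k covariates: 1 + k/(N − k − 3). At N = 24, k = 1 this is 1.05. At N = 81, k = 4 (baseline and the three stratification factors) it is 1 + 4/74 = 1.054.
- Half-width = t × √(variance × factor) × √(1/n₁ + 1/n₂), with no finite-sample factor for raw change. Degrees of freedom are N − 2 for raw change and N − k − 2 for the model.

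At 16 vs 8, √(1/16 + 1/8) = 0.433; t is 2.074 (22 df) for raw change and 2.080 (21 df) for the model.

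| rho | Raw change | Adjusted, one baseline |
|---|---|---|
| 0.5 | 2.074 × √1.00 × 0.433 = 0.898 | 2.080 × √(0.75 × 1.05) × 0.433 = 0.799 |
| 0.7 | 2.074 × √0.60 × 0.433 = 0.696 | 2.080 × √(0.51 × 1.05) × 0.433 = 0.659 |
| 0.9 | 2.074 × √0.20 × 0.433 = 0.402 | 2.080 × √(0.19 × 1.05) × 0.433 = 0.402 |

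At 54 vs 27 and rho 0.7 the half-width goes from 0.363 to 0.344.

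**3. Unusable recordings.** A simulation made each recording independently usable with a fixed probability, at rho 0.7. With 80% usable, the mean half-width goes from 0.81 to 0.77 (starting from 16 vs 8) and from 0.42 to 0.40 (from 54 vs 27). With 60% usable it goes from 1.03 to 1.02 and from 0.52 to 0.51, so almost nothing is gained.

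**4. How many covariates at the interim.** With the three stratification factors as well (k = 4, N = 24), the finite-sample factor is 1 + 4/17 = 1.235 instead of 1.05. Unless those factors explain much of the variance, pre-dose power alone is the better choice there.

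**5. Is there a second pre-dose recording?** Table 1 marks EEG at the Baseline visit and on Day 1. Section 8.10 has the first qEEG block end when the morning meal starts, with blocks at a similar time at each visit. Section 4.1 puts dosing after the start of a meal. A Day 1 pre-dose block is therefore likely. It remains an inference, because the body of Table 2, which sets the qEEG timings, is not in the available text.

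**6. Would averaging two pre-dose recordings help?** If both predict the outcome equally well, the residual variance is 1 − 2rho²/(1 + rho). That is 0.89, 0.83 and 0.78 of the one-baseline value at rho 0.5, 0.7 and 0.9. Now suppose the correlations are 0.8 (outcome with Day 1 block), 0.5 (outcome with Baseline visit) and 0.5 (between the two):

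- Mean of two: 1 − 0.65²/0.75 = 0.437
- Day 1 block alone: 1 − 0.8² = 0.36
- Ratio: 0.437/0.36 = 1.21

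The standard errors at 16 vs 8 are then 0.293 for the mean of two, 0.274 for raw change, 0.266 for the Day 1 block alone, and 0.268 with both entered as separate covariates. In this case averaging does worse than raw change.

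**The case against.** The strongest objection is that an adequate method may already exist. The primary-endpoint method in Section 9.3.2 is redacted. A later sentence there extends it to continuous endpoints, and the abbreviation list includes a repeated-measures mixed model. Sections 4.1.2.2, 9.3.2 and 9.5 place detailed methods in sponsor documents written before each analysis. Section 9.3.5 carries no redaction mark, but text is missing unmarked elsewhere (a list in Section 4.1.2.2 starts at its second item), so its completeness cannot be proved. All of this stands. On the other side, the sentence on continuous endpoints follows one about efficacy endpoints, and pharmacodynamics has its own section. A cross-reference would settle the matter.

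Two stronger readings are tempting. A reader might infer that the trial has no inferential qEEG analysis, or that a stopping recommendation would rest on the descriptive output of Section 9.3.5. The documents show neither, because the interim method sits in a separate technical document. A reader might also infer that Section 9.3.1 wastes a Baseline-visit recording and that averaging all pre-dose recordings must be more precise. The second recording is only inferred, Section 9.3.1 does not bar its use in the planned exposure-qEEG analyses, and step 6 shows that averaging can reduce precision. Taking the latest pre-dose value is a recognised convention.

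**Conclusion.** The point holds in a limited form. The visible Section 9.3.5 does not deliver the between-arm test that other sections promise, and the qEEG baseline recording is not clearly identified. The main benefit of the change is a stated difference with a 95% CI. The gain in precision over raw change is modest: at 16 vs 8 the half-width shrinks by about 11% at rho 0.5 (0.898 to 0.799), by about 5% at rho 0.7 (0.696 to 0.659), and not at all at rho 0.9. It also fades when many recordings are unusable. These sizes rest on assumed correlations and equal variances, which the documents do not give. If the redacted or filed method already covers qEEG, only the cross-reference and the baseline clarification remain. Priority is low to moderate.

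**What to change.** 1. Add to Section 9.3.5, alongside the existing summaries: *Beta-band power at Day 2 and at Day 14 will be compared between basmisanil and placebo with a linear model (or the primary-endpoint model, if it applies) adjusted for pre-dose beta-band power. The difference will be reported with a 95% CI. The final analysis will also include age group, copy number and epilepsy; the interim analysis will adjust for pre-dose beta-band power only.* If the redacted method already does this, a cross-reference is enough.
2. State in Sections 8.6.2 and 9.3.1, and in the interim technical document, which pre-dose recording is the qEEG baseline: the Baseline-visit recording or the Day 1 pre-dose block, if Table 2 schedules one.
3. Do not average the two. At most, if both exist, enter both as separate covariates in the final analysis.

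The cost is protocol wording, routine programming and one degree of freedom for the covariate at the interim. No new data are needed.

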## **9.4 STATISTICAL ANALYSES OF PART 2**

*Analyses using the complete database including both Parts 1 and 2 of the study will be performed when all participants complete the protocol-defined assessments or are prematurely withdrawn. Details on the statistical methodology will be described in a separate technical document prior to the analysis.*

## **9.5 INTERIM ANALYSES**

Interim analyses in Part 1 will be conducted as described in Section 4.1.2.2.

A first interim analysis is planned once approximately 24 participants (Stage 1 and Stage 2) have completed 4 weeks of treatment or withdrawn from treatment prior to that.

The Sponsor may choose to conduct an additional interim analysis *during Part 1*. The decision to conduct an optional interim analysis and the timing of the analysis will be documented in the Sponsor's trial master file prior to the conduct of the interim analysis.

The interim analyses will be performed and interpreted by members of the IMC and *may be shared with the SOC as needed and as described in Section 4.1.2*. Access to treatment assignment information will follow the Sponsor's standard procedures.

All statistical analysis methodologies will be described in detail and documented in the Sponsor's trial master file prior to performing any of the planned interim analyses.

*After completion of the primary analysis of Part 1 and prior to the end of the study, the Sponsor may conduct additional interim analyses combining the data collected in both Part 1 and Part 2. The timing of and the methods used in such analyses will be documented in the Sponsor's trial master file prior to the analysis.*

## **9.6                   SUMMARIES OF CONDUCT OF STUDY**

Protocol deviations will be summarized by treatment group; a participant listing will also be available.

Participant disposition, including number of participants randomized and discontinuations from study treatment or study will be reported.

Terms for concomitant medications recorded on the eCRF by the Investigator will be mapped to preferred terms by the Sponsor. Data on concomitant medication will be summarized and listed.

## **Appendix 1** **Regulatory, Ethical, and Study Oversight Considerations**

### **1. REGULATORY AND ETHICAL CONSIDERATIONS**

#### **1.1. COMPLIANCE WITH LAWS AND REGULATIONS**

This study will be conducted in full conformance with the ICH E6 guideline for Good Clinical Practice and the principles of the Declaration of Helsinki, or the laws and regulations of the country in which the research is conducted, whichever affords the greater protection to the individual. The study will comply with the requirements of the ICH E2A guideline (Clinical Safety Data Management: Definitions and Standards for Expedited Reporting). Studies conducted in the United States or under a U.S. Investigational New Drug (IND) application will comply with U.S. FDA regulations and applicable local, state, and federal laws. Studies conducted in the EU/EEA will comply with the EU Clinical Trial Directive (2001/20/EC) or *Clinical Trials Regulation (536/2014) (EEA sites only)*, and all other applicable local regulations.

#### **1.2. INSTITUTIONAL REVIEW BOARD OR ETHICS COMMITTEE**

This protocol, the ICFs, any information to be given to the participant or caregiver (e.g. advertisements, diaries, etc.), and relevant supporting information must be submitted to the IRB/EC by the Principal Investigator and reviewed and approved by the IRB/EC before the study is initiated. In addition, any participant recruitment materials must be approved by the IRB/EC.

The Principal Investigator is responsible for providing written summaries of the status of the study to the IRB/EC annually or more frequently in accordance with the requirements, policies, and procedures established by the IRB/EC. Investigators are also responsible for promptly informing the IRB/EC of any protocol amendments (Section 2.3.1 of this appendix).

The Investigator should follow the requirements for reporting all adverse events (AEs) to the Sponsor. Investigators may receive written IND safety reports or other safety-related communications from the Sponsor. Investigators are responsible for ensuring that such reports are reviewed and processed in accordance with Health Authority requirements and the policies and procedures established by their IRB/EC, and archived in the site's study file.

#### **1.3. INFORMED CONSENT**

The Sponsor's Master Informed Consent Form *including the consent form for the optional open-label extension part of the study* (and ancillary sample ICFs such as a Child's Assent or Caregiver's Informed Consent Form, if applicable) will be provided to each site. If applicable, it will be provided in a certified translation of the local language. Participant's *caregiver or participant's legally authorized representative* must be informed that participation is voluntary. Participant's *caregiver or legally authorized*

representative will be required to sign a statement of informed consent that meets the requirements of 21 CFR 50, local regulations, ICH guidelines, Health Insurance Portability and Accountability Act (HIPAA) requirements, where applicable, and the IRB/IEC or study center. The Sponsor or its designee must review and approve any proposed deviations from the Sponsor's sample ICFs or any alternate consent forms proposed by the site (collectively, the "Consent Forms") before IRB/EC submission. The final IRB/EC-approved Consent Forms must be provided to the Sponsor for Health Authority submission purposes according to local requirements. Participant's *caregiver or participant's legally authorized representative* must be re-consented to the most current version of the ICF(s) during the *participant's* participation in the study. A copy of the ICF(s) signed by all parties must be provided to the *participant's caregiver* or the participant's legally authorized representative.

*Due to the nature of Dup15q syndrome, participants in this study will not be asked to provide their own informed consent. The Informed Consent Form included in this study is for the caregiver or the legally authorized representative of the participant. The participant's ability to provide assent will not be dependent on their age. Assent should be obtained for all participants who, in the opinion of the Investigator, are judged capable of giving assent.*

The ICFs must be signed and dated by the participant's *caregiver or legally authorized representative* before *the participant's* participation in the study. The case history or clinical records for each participant shall document the informed consent process *from the caregiver or participant's legally authorized representative* and that written informed consent was obtained prior to participation in the study.

The ICFs should be revised whenever there are changes to study procedures or when new information becomes available that may affect the willingness of the participant's *caregiver or participant's legally authorized representative* to take part. The final revised IRB/EC-approved ICFs must be provided to the Sponsor for Health Authority submission purposes if required as per local regulations.

If the ICFs are revised (through an amendment or an addendum) while a participant is participating in the study, the participant's *caregiver* or a legally authorized representative may be re-consented by signing the most current version of the ICFs or the addendum, in accordance with applicable laws and IRB/EC policy. For any updated or revised ICFs, the case history or clinical records for each participant shall document the informed consent process and that written informed consent was obtained using the updated/revised ICFs for continued participation in the study. The study team will provide guidance for which participants need to re-consent in the event of an update to the ICF.

A copy of each signed ICF must be provided to the participant's *caregiver or participant's* legally authorized representative. All signed and dated ICFs must remain in

each participant's study file or in the site file and must be available for verification by study monitors at any time.

If a participant is re-screened, the caregiver *or the participant's legally authorized representative* is not required to sign another ICF if the re-screening occurs within 30 days from the previous ICF signature date.

